5.5.5. Exposure to Investigational Product

Patients will receive the investigational medicinal product (IMP) at the following planned time points:

- Beginning of Month 1 (Visit 3)
- Beginning of Month 2 (Visit 5)
- Beginning of Month 3 (Visit 6)

- Beginning of Month 4 (Visit 7)
- Beginning of Month 5 (Visit 8)
- Beginning of Month 6 (Visit 10)

The following information will be recorded on the eCRF for each dose:

- Confirmation that the patient received the IMP (including reason if the IMP was not given)
- Date and time of administration

The following will be derived from the information recorded on the eCRF:

- For treatment phase (SP III), duration of exposure in days is calculated as treatment phase disposition date first date IMP administered +1.
- For treatment phase (SP III), number and percentage of patients with 1, 2 and 3, 4, 5, or 6 doses injected.

Comparisons between treatments for duration of IMP exposure will be performed using an ANOVA with treatment in the model. Number of patients with 1 dose, 2, 3, 4, 5 or 6 doses injected will be compared between treatment groups with Fisher's exact test.

In addition, injections not administered will be listed.

5.5.6. Treatment Compliance

Treatment compliance will be calculated for Study Period III as:

number of doses received * 100 number of intended doses

Comparisons between treatments for treatment compliance will be performed using an ANOVA with treatment in the model. For this analysis, partial dose (for example, a patient only got 1 injection instead of 2) will be considered as no dose received.

5.5.7. Electronic Patient Reported Outcomes Diary Compliance

Electronic patient reported outcomes diary compliance at each 1-month period (including baseline, Month 1, 2, 3, ... till Month 10) as well as for SP III overall (Month 1 through Month 6) will be calculated. Diary compliance at each period is calculated as:

 $\frac{\text{Actual number of diary days in the period}}{\text{Expected number of diary days in the period}}*100$

Expected number of Diary days is calculated as date of injection (date of visit for post-treatment follow-up phase) at the end of interval minus date of injection (date of visit for post-treatment follow-up phase) at the beginning of the interval +1.

Treatment comparisons for diary compliance for each period will be performed separately using an ANOVA with treatment and pooled region1 in the model.

5.5.8. Previous Migraine Prevention Therapy

The proportion of patients who received previous migraine prevention therapy, and the proportion of patients with response to the previous migraine prevention therapy within each of the 6 categories (to enter this trial, medical history event, adequate response, inadequate response, no response, and treatment availability) will be summarized for all ITT patients. Treatment group comparisons will be done using Fisher's exact test. Previous migraine prevention therapies are those therapies that started prior to the date of the first injection and stopped prior to or at the date of first injection and indication is "primary study condition" or corresponding medical history event preferred term that includes "migraine".

5.5.9. Concomitant Therapy

The proportion of patients who received concomitant medication collected from eCRF as well as abortive medications collected through ePRO will be summarized for all ITT patients for Study Period III and Study Period IV separately. Concomitant therapies for Study Period III are those which stopped or continued in Study Period III. If medication started and stopped on the same day of injection, it will still be considered as concomitant medication for SP III. If a medication started before the first day of injection but stopped on the same day of injection, then it will not be counted as concomitant medication for SP III. Concomitant therapies for Study Period IV are those which either started, stopped or continued in Study Period IV.

Treatment group comparisons will be done using Fisher's exact test for Study Period III with ITT population. Descriptive statistics only will be presented for the treatment groups in Study Period IV with post-treatment population.

5.5.10. Efficacy Analyses

5.5.10.1. Primary Outcome and Methodology

The primary efficacy objective is to assess whether at least 1 dose of LY2951742 (120 or 240 mg/month) is superior to placebo in the prevention of migraine headache in patients with episodic migraine.

The primary analysis will evaluate the efficacy of LY2951742 (120, or 240 mg/month) compared with placebo on the overall mean change from baseline in the number of monthly migraine headache days during the 6-month treatment phase.

The primary analyses will be performed using a restricted maximum likelihood (REML)-based mixed models repeated measures (MMRM) technique. The analysis will include the fixed categorical effects of treatment, pooled region1, month, and treatment-by-month interaction, as well as the continuous fixed covariates of baseline number of migraine headache days and baseline-by-month interaction.

An unstructured covariance structure will be used to model the within-patient errors. The Kenward-Roger (Kenward and Roger 1997) approximation will be used to estimate denominator

degrees of freedom. If the model does not converge with both the Hessian and the G matrix being positive definite under the default fitting algorithm used by PROC MIXED, the Fisher scoring algorithm will be implemented by specifying the SCORING option in SAS. If the model still fails to converge, the model will be fit using covariance matrices of the following order specified by a decreasing number of covariance parameters until convergence is met:

- Heterogeneous Toeplitz
- Heterogeneous First-order autoregressive
- Toeplitz
- First-order autoregressive

When the unstructured covariance matrix is not utilized, the sandwich estimator (Diggle and Kenward 1994) will be used to estimate the standard errors of the fixed effects parameters. The sandwich estimator is implemented by specifying the EMPIRICAL option in SAS[®]. When the sandwich estimator is utilized, the Kenward-Roger approximation for denominator degrees of freedom cannot be used. Instead, the denominator degrees of freedom will be partitioned into between-subject and within-subject portions by the DDFM=BETWITHIN option in SAS[®]. SAS[®] PROC MIXED will be used to perform the analysis.

The primary endpoint of this study for each LY2951742 dose arm compared with placebo will be estimated as the main effect of treatment from the MMRM analysis during the 6-month treatment phase. This provides the average treatment effect across 6 months of double-blind treatment phase. The repeated-measures analysis will include data from all 3 treatment groups. The Type I error rate for the study will be controlled at a 2-sided 0.05 level (equivalently, one-sided 0.025 level). Specific details of the testing procedure for the primary outcome and the secondary gatekeeper objectives are provided in Section 5.5.10.4.

The results of the statistical tests at each month in the double-blinded treatment phase from the primary analysis model will be used to assess the onset of effect for each LY2951742 dose arm compared with Placebo. In particular, if the primary efficacy analysis is statistically significant, then the earliest month when statistical significance is observed and maintained for all the subsequent months during double-blinded treatment phase will be considered as the onset of effect.

5.5.10.2. Sensitivity Analysis for Primary Outcome

Two types of sensitivity analyses are planned to assess the robustness of deviations from the assumptions of primary analysis including normality assumption and missing data assumption. Another sensitivity analysis is planned to explore the influence of slight change in the definition of episodic migraine prevention.

Missing Data Assumption

Sensitivity analyses will be performed to assess the robustness of the primary analysis conclusions to deviations from missing at random (MAR) assumption. The approach for these analyses is to vary the assumptions of missing data for the primary analysis in a systematic way.

Basically, the method will be to predict the missing outcomes and then add values (Δ_{120} , Δ_{240} , Δ_{P}) to the predictions in the LY2951742 120 mg/month, LY2951742 240 mg/month, and placebo treatment groups respectively, regardless of the reason the data are missing. This approach is consistent with the sensitivity approach suggested in Permutt (2015). This procedure will be repeated multiple times for different values of (Δ_{120} , Δ_{240} , Δ_{P}) using the following steps:

- 1) Predict the missing outcomes for each treatment via multiple imputation based on observed primary endpoint and baseline values. Such imputation will be carried out using a Markov Chain Monte Carlo method with a Jeffreys prior via SAS® PROC MI. Thirty (30) such imputations will be created.
- 2) Add the corresponding Δ value (i.e. $\Delta_{120}, \Delta_{240, \text{ or }} \Delta_P$) to the imputed values based on the patient treatment group.
- 3) Conduct the primary analysis separately for each of the 30 imputations.
- 4) Combine the results of these analyses using Rubin's combining rules, as implemented in SAS® PROC MI ANALYZE.

The above steps will be repeated multiple times for different values of $(\Delta_{120}, \Delta_{240}, \Delta_P)$ with Δ_P ranging from (0, twice the absolute value of the mean value seen for placebo in the primary analysis) and both Δ_{120} and Δ_{240} ranging from (Δ_P , Δ_P + absolute value of the biggest mean treatment difference seen within the primary analysis). For example, if the overall mean change from baseline for placebo is -3.6 and the maximum overall treatment difference is -1.5, then Δ_P would range from (0,7.2) and Δ_{120} and Δ_{240} would range from (Δ_P , Δ_P + 1.5).

Normality Assumption

To assess the robustness of the MMRM results to deviations from normality assumption, a sensitivity analysis for the raw number of migraine headache days (the total number of migraine headache days for each interval without normalization to 30-day period) will be conducted with a repeated measures negative binomial regression analysis fitted with SAS PROC GLIMMIX. The model will include treatment, pooled region1, month, and treatment-by-month interaction, as well as the continuous fixed covariates of baseline number of monthly migraine headache days and baseline-by-month interaction, log (number of compliant calendar days within each month/30) as the offset in the model. In case of non-convergence, pooled region1 and/or baseline-by-month interaction may be excluded from the model. Directional consistency of treatment effects from this model and the primary analysis MMRM model as specified in Section 5.5.10.1 will be examined.

In addition, as another form of sensitivity analysis, residuals from the primary analysis MMRM model will be examined and outliers identified. Consistency of results before and after removing patients with outlier residuals will be examined.

Definition of Episodic Migraine Headache

This sensitivity analysis is to assess the robustness of the primary results to the deviation of minor change in the definition of migraine (See C. below). It is implemented by repeating the primary analysis using the number of monthly migraine headache days derived based on the

following definition of migraine, which aligns with migraine headache days definition in chronic migraine, but is considered relevant for the episodic population, as well.

A headache, with or without aura, of \geq 30 minutes duration with both of the following required features (A and B):

- A. At least 2 of the following headache characteristics:
 - Unilateral location
 - o Pulsatile quality
 - o Moderate or severe pain intensity
 - o Aggravation by or causing avoidance of routine physical activity

AND

- B. During headache at least one of the following:
 - o Nausea and/or vomiting
 - o Photophobia and phonophobia

OR

C. Patient takes a triptan or ergot derivative.

5.5.10.3. Secondary and Exploratory Efficacy Analyses

Table 5.6 summarizes all the planned secondary and exploratory efficacy analyses for Study Period III and Study Period III/IV. All response rates are derived from migraine headache days.

Continuous Efficacy Measures

For the continuous efficacy measures, the change from baseline to each post-baseline period will be estimated for each treatment from repeated measures analyses as described for analysis for primary outcome.

For the continuous secondary efficacy measures where the objective is to assess overall mean change during 6-month treatment phase, the endpoint for comparing LY2951742 with placebo will be estimated as the main effect of treatment from the MMRM analysis across Months 1-6.

In addition to the repeated measures analyses, the mean change from baseline to the average monthly measures during 6-month treatment phase or LOCF endpoint in study period III will be estimated for the continuous efficacy measures using ANCOVA models with covariates adjustment described in Section 5.5.1.1.

Binary Efficacy Measures

For the repeated binary efficacy measures such as responder indicators based on the number of migraine headache days, the visit wise binary responder indicators will be analyzed using a categorical, pseudo-likelihood-based repeated measures analysis. This analysis will be implemented using the GLIMMIX procedure in SAS to compare treatments and include the fixed, categorical effects of treatment, month, and treatment-by-month interaction, as well as the continuous, fixed covariate of baseline value.

An unstructured covariance structure will be used to model the within-patient errors (denoted by TYPE=CHOL in the RANDOM statement). The Newton-Raphson method with ridging will be used for nonlinear optimization (denoted by including NLOPTIONS TECH=NRRIDG). The Kenward-Roger approximation will be used to estimate denominator degrees of freedom. If the model does not converge, the Fisher scoring algorithm will be utilized by the SCORING option in SAS.

If the model still fails to converge, the model will be fit using covariance matrices in the following order specified by a decreasing number of covariance parameters until convergence is met.

- Heterogeneous Toeplitz,
- Heterogeneous autoregressive,
- Toeplitz, and
- Autoregressive.

If necessary, both fitting algorithms will be used in the pre-specified order before proceeding to the next covariance structure in the sequence.

For models where the unstructured covariance matrix is not utilized, the sandwich estimator (Diggle et al. 1994) will be used to estimate the standard errors of the fixed effects parameters. The sandwich estimator is utilized by the EMPIRICAL option in SAS. When the sandwich estimator is utilized, the Kenward-Roger approximation for denominator degrees of freedom cannot be used. Instead, the denominator degrees of freedom will be partitioned into between-subject and within-subject portions by the DDFM=BETWITHIN option in SAS.

For the repeated binary secondary efficacy measures where the objective is to assess the proportion of patients with X% response during the 6-month double-blind treatment phase, the endpoint for comparing LY2951742 with placebo will be estimated as the main effect of treatment from the categorical MMRM analysis across Months 1-6.

For visit wise indicators of 50% responders, the results of the statistical tests at each month in the double-blinded treatment phase from categorical MMRM analysis will be used to assess the onset of 50% sustained response for LY2951742 compared to Placebo. In particular, if the key secondary measure of 50% response rate is statistically significant, then the earliest month where the statistical significance is observed and maintained for all the subsequent months during double-blinded treatment phase will be considered as the onset of 50% sustained response.

For non-repeated binary measures, such as 50% response sustained for three consecutive months until patient's endpoint in 6-month treatment phase and 50% response sustained from Month 1 to Month 6, a logistic regression analysis with covariates of treatment, baseline and pooled region 1 will be conducted.

Measures Conditional on the Post-baseline Number of Migraine Headache Days > 0

The following measures are conditional on the number of migraine headache days >0:

- Mean severity of remaining migraine on migraine headache days
- Proportion of migraine headache days with abortive (acute) medication use

They will be modelled individually using MMRM model, assuming data are missing during months without migraine headache.

Analyses for Number of Weekly Migraine Headache Days in Month 1

The number of weekly migraine headache days in Month 1 can be considered as ordinal data with possible values of 0, 1, 2, 3, 4, etc. It will be analyzed using an ordinal repeated measures model implemented using the GLIMMIX procedure in SAS. In this model, a proportional odds model with cumulative logit link will be used, and a random intercept will be applied to the observations for each patient to account for repeated measures. The model will include the fixed, categorical effects of treatment, pooled region1, week, and treatment-by-week interaction, as well as the continuous, fixed covariate of baseline number of migraine headache days and baseline number of migraine headache days by week interaction. Log (number of compliant calendar days within each week/7) will be used as the offset in the model.

Time to Event Measures

For the following time to event measures, a Kaplan-Meier curve of the time to event and treatment group comparison using log-rank test stratified by pooled region1 and baseline MHD frequency category (<8 vs ≥8 migraine headache days per 30-day period) will be provided.

- Time to first 50% response in double-blind treatment phase
- Time to first loss of 50% response in post-treatment phase
- Time to initiation of preventative treatment for migraine or probable migraine in post-treatment phase

Distribution of Response Rates

Overall x% response rate during the double-blind treatment phase will be estimated for X=0, 5, 10, ..., 95, and 100, using GLIMMIX model as described earlier in this section. These estimated response rates will be plotted and points within each treatment arm will be connected to show a curve of response rates. No statistical comparisons will be conducted among different treatment arms.

Analysis for PGI-I

The PGI-I raw value will be analyzed with a mixed model repeated measures analysis where the covariates are the fixed categorical effects of treatment, visit, and treatment-by-visit interaction, as well as the continuous fixed covariates of baseline PGI-S score and baseline PGI-S score-by-visit interaction.

Table 5.6. Secondary and Exploratory Efficacy Variables and Analysis Methods

Efficacy Variables	Analysis in SP III	Analysis in SP III/IV
Number of migraine headache hours		
Number of migraine attacks		
Number of migraine headache days with abortive (acute)		
medication use		
Proportion of migraine headache days with abortive (acute)		
medication use	MMRM,	
Number of headache days	ANCOVA ^a	
Number of moderate-severity headache days		
Number of headache hours		
Number of ICHD migraine headache days		
PGI-S		
PGI-I (adjusting for PGI-S)		
Average Pain Score for non-migraine chronic pain		
Mean severity of migraine headache		
Number of migraine headache days with nausea and/or		
vomiting		
Number of migraine headache days with photophobia and		
phonophobia		
Number of migraine headache days with aura		
Number of migraine headache days prodrome symptoms		
other than aura		
Number of non-migraine headache days with aura		
Proportion of aura among migraine attacks		
Number of days with abortive medication use		MMRM for SP
Number of classes of abortive medication use	MMRM	III/IV
Number of classes of abortive medication use on migraine		111/1 (
headache days	_	
Average number of classes of abortive medications use		
Average number of classes of abortive medications use on		
migraine headache days	_	
Number of days with triptans use	_	
Number of migraine headache days with triptan use	_	
Number of days with NSAIDs/aspirin use		
Number of migraine headache days with NSAIDs/aspirin		
use		

Secondary and Exploratory Efficacy Variables and Analysis Methods (cont)

Efficacy Variables	Analysis in SP III	Analysis in SP III/IV
Number of days with NSAIDs/aspirin use		
Number of migraine headache days with NSAIDs/aspirin		
use		
Number of days with acetaminophen/paracetamol use		
Number of migraine headache days with		
acetaminophen/paracetamol use		
Number of days with ergots use		
Number of migraine headache days with ergots use		
Number of days with anti-nausea medication use		
Number of migraine headache days with anti-nausea		
medication use		
Number of days with Multi-Class abortive medication use		
Number of migraine headache days with multi-class		
abortive medication use		
Average number of abortive medication classes		
Average number of abortive medication classes on migraine		
headache days	CI D O OV	CL D O GV
X% response rate (X=30, 50, 75, or 100) (visit wise)	GLIMMIX	GLIMMIX
50% response sustained for 3 consecutive months until	Logistic regression	NA
patient's endpoint in 6-month treatment phase		
50% response sustained from month 1 to month 6	ar n n arr	
Distribution of managements in CD III	GLIMMIX (to get	NI/A
Distribution of response rate in SP III	estimated response rates)	N/A
	Kaplan-Meier	
Time to first 50% response in SP III	curve and stratified	N/A
Time to first 3070 response in St. III	log-rank test	14/11

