# Appendix 2. Schedule of Activities

Schedule of Activities, Protocol I5Q-MC-CGAH

Study Period (SP)	SP I- Screening	SP II- Prospective Baseline		SP III - Treatment										SP IV – Follow-up		
(Target) Interval (days) since previous visit			30-45	14	16	30	30	30	15	15	15	15	60	60		
Allowable range (days) between visits	3-45	30-40 a														
Interval allowance (days)				+/- 1	+/- 3	+/- 2	+/- 2	+/- 2	+/- 2	+/- 2	+/- 2	+/- 2	+/- 5	+/- 5	ET	
Visit	1	2	3	4 b	5	6	7	8	9°	10	11°	12	13	14		
Month			0	0.5	1	2	3	4	4.5	5	5.5	6	8	10		
Assessments and Procedur	es															
Informed consent	X															
Inclusion/exclusion	X	X	X													
Demographics	X															
Physical examination	X															
Neurological examination d	X						X					X		X	X	
Height	X															
Weight	X											X		X	X	
Waist and hip circumference	X															
Medical history	X															
Pre-specified migraine history		X														

Visit	1	2	3	4 b	5	6	7	8	9°	10	11 c	12	13	14	ET
Month			0	0.5	1	2	3	4	4.5	5	5.5	6	8	10	
Substance use	X														
ECGe	X		X									X		X	X
Vital signsf	X		X		X	X	X	X		X		X	X	X	X
Adverse events	X	X	X	X	X	X	X	X		X		X	X	X	X
Concomitant medications	X	X	X		X	X	X	X		X		X	X	X	X
ePRO training		X													
ePRO daily patient entries		X	X	X	X	X	X	X	X	X	X	X	X	X	X
Patient training video			X												
Clinical Laboratory Tests a	and Samplin	g Schedules					•								
Hematology	X		X				X					X		X	X
Clinical chemistry	X		Xg				Xg					Xg		Xg	Xg
HDL	X		Xg				Xg					Xg		Xg	Xg
HbA1c			X									X		X	X
Fasting insulin/ fasting C-peptide			X g									$X^{g}$			X g
Urinalysis h	X		X									X		X	X
Serum Pregnancy (for women of childbearing potential) or FSH at Visit 1 (all other female patients) i	X											X		X	Х
Urine pregnancyi			X		X	X	X	X		X					
Urine drug screen	X														

Visit	1	2	3	4 b	5	6	7	8	9°	10	11°	12	13	14	ET
Month			0	0.5	1	2	3	4	4.5	5	5.5	6	8	10	
Immunogenicity i			X	X	X	X	X					X		X	X
Biomarker storage sample	X	X	X		X		X			X				X	X
CCI															
PK blood sample j				X	X	X	X	X	X	X	X	X	X	X	X
CCI															
RNA			X									X		X	
Study drug administered k			X		X	X	X	X		X					
Scales, Questionnaires, and	d Outcome M	leasures													
MIDAS			X				X					X		X	X
MSQ v2.1			X		X	X	X	X		X		X		X	X
Non-migraine chronic pain assessment 			X				X					X			X

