- Number of weekly migraine headache days in Month 1 is calculated as the number of migraine headache days in a 7-day period on which a migraine headache occurs. At Month 1, the first 7 calendar days will be counted as week 1, the second 7 calendar days will be counted as week 2, the third 7 calendar days will be counted as week 3, the rest of the calendar days will be counted as week 4.

Combination medications (such as aspirin/acetaminophen/caffeine) will be counted in each medication category that applies (such as NSAIDs/aspirin and Acetaminophen/paracetamol).

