		Missing safety measurement: Chemistry or Hematology at baseline or double-blind treatment phase	Programmable – Stats	For randomized patients with non-missing Visit 7 date, if calcium and hemoglobin are missing all baseline or missing all post-baseline measures during double blind treatment phase. For patients who discontinued early, as long as they have one post-baseline lab measures, it is not an important protocol deviation. For patients who discontinued due to "lost to follow up", if all post-baseline measures are missing, it is not protocol deviation.
		Missing safety measurement: Chemistry or Hematology at post- treatment phase	Programmable – Stats	For patients who completed or discontinued (due to reasons other than "lost to follow up") post-treatment phase, if calcium and hemoglobin is missing all postbaseline measures during the post-treatment phase. For patients who discontinued due to "lost to follow up" at post treatment phase, if all post-baseline measures are missing, it is not protocol deviation.

Category	Subcategory	Study-specific	Source	Methods of Identification
Data Quality	Other	Missing safety measurement: ECGs at baseline or double-blind treatment phase.	Programmable – Stats	For randomized patients, if ECGs are missing all baseline, or if there is non-missing Visit 12 date and missing all post-baseline measures during the double blind treatment phase.
Study Procedures	Excluded Conmeds	Taking prohibited migraine preventive medication for primary indication only for >7 consecutive days during Study Period II or III	Programmable - Stats	Prior therapy should be excluded in the consideration.
		Taking prohibited medication for any indication for >7 consecutive days during Study Period II or III	Programmable - Stats	Prior therapy should be excluded in the consideration.
		Taking Botulinum toxin A and B for any indication during Study Period II or III	Non-Programmable- Study Team identified	 Stats will create the list of patients meet this IPD criteria. Among those, the true IPDs will be manually added into non-programmable excel sheet
		Opioids, barbiturates use >7 consecutive days during Study Period II or III	Programmable – Stats	Prior therapy should be excluded in the consideration.
	Visit schedule criteria	Dosing interval outside specified limits	Programmable – Stats	For randomized patients, compare dosing interval to allowable visit intervals between doses. Allowable dosing intervals: 21 to 37 days

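### The weekly Month 1 migraine-day model puts a log-days offset under a cumulative logit, where it only partly corrects for days observed and its direction is not stated

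*SAP*

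**What the plan says.** SAP 5.4.1 defines the weekly measure as "the number of migraine headache days in a 7-day period on which a migraine headache occurs". It then forms three blocks of 7 days from the start of Month 1, after which "the rest of the calendar days will be counted as week 4".

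SAP 5.5.10.3 says that the weekly count "can be considered as ordinal data with possible values of 0, 1, 2, 3, 4, etc" and that "a proportional odds model with cumulative logit link will be used", with a random intercept per patient. Week and treatment-by-week enter as categorical effects. The adjustment for diary days is: "Log (number of compliant calendar days within each week/7) will be used as the offset in the model". Neither section says whether the logits are for higher or lower counts, or what happens to a week with no compliant days, where the logarithm is undefined.

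The normality sensitivity analysis in SAP 5.5.10.2 uses the same kind of offset, log(compliant days/30), in a different model for the raw monthly count: a "repeated measures negative binomial regression analysis fitted with SAS PROC GLIMMIX".

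Protocol Appendix 2 sets Visit 4 at 14 days (±1) after Visit 3, and Visit 5 at 16 days (±3) after Visit 4. SAP Appendix Table 1 flags dosing intervals as deviations against this limit: "Allowable dosing intervals: 21 to 37 days".

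**The concern.** A log-exposure offset belongs with a log link: twice the days, twice the expected count. Under a cumulative logit, the same term adds one fixed amount to the log-odds at every threshold. That is not what observing more days does to the probability of reaching a given count. If the logits are for lower counts, a positive offset for a longer week also pushes the model the wrong way.

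Two things are at stake. If the number of observed days differs between arms, part of that difference appears as a treatment effect. And because week 4 is usually longer than 7 days, it is not on the same footing as weeks 1 to 3.

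**Working it through.** The SAP gives no power, sample size or alpha for this analysis, so there is no stated figure to reproduce.

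**Inputs.** The offset is log(n/7), coefficient 1, with n compliant days (SAP 5.5.10.3). The daily probability p is an assumption: 4/30, 8/30 and 14/30, from the eligibility limits (Protocol 5.1) and the stratification cut (Protocol 6.2). Days are taken as independent, so Y ~ Binomial(n, p).

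**Step 1: log link.** E(Y) = n × p, so log E(Y | n) − log E(Y | 7) = log(n/7). The offset is exact for every n and p.

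**Step 2: cumulative logit.** The shift needed at threshold k is logit P(Y ≥ k | n) − logit P(Y ≥ k | 7). Example with p = 4/30, k = 1:
- 7 days: P = 1 − (26/30)^7 = 0.633, logit 0.544.
- 9 days: P = 1 − (26/30)^9 = 0.724, logit 0.965.
- Shift needed 0.965 − 0.544 = 0.42; offset supplied log(9/7) = 0.25.

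| Days | Offset | p | Y≥1 | Y≥2 | Y≥3 | Y≥4 |
|---|---|---|---|---|---|---|
| 9 | +0.25 | 4/30 | 0.42 | 0.51 | 0.73 | 1.08 |
| 9 | +0.25 | 8/30 | 0.68 | 0.65 | 0.73 | 0.95 |
| 9 | +0.25 | 14/30 | 1.27 | 1.10 | 1.01 | 1.03 |
| 5 | −0.34 | 4/30 | −0.50 | −0.69 | −1.08 | −1.73 |
| 5 | −0.34 | 8/30 | −0.74 | −0.78 | −1.03 | −1.55 |
| 5 | −0.34 | 14/30 | −1.29 | −1.15 | −1.17 | −1.45 |

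The offset is too small in every cell, and the need varies with rate and threshold, so no fixed offset is exact. Poisson counts give the same picture (0.41 to 0.96 for 9 days; −0.49 to −1.15 for 5).

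**Step 3: arms with different observed days and no treatment effect.** Proportional odds fits for one week, 40,000 simulated patients per arm, counts of 5 or more grouped, no random intercept. Entries are false log odds ratios.

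| Days | p | No offset | Offset toward higher counts | Offset toward lower counts |
|---|---|---|---|---|
| 7 vs 5 | 4/30 | −0.56 | −0.22 | −0.89 |
| 7 vs 5 | 8/30 | −0.84 | −0.50 | −1.18 |
| 7 vs 5 | 14/30 | −1.31 | −0.97 | −1.65 |
| 7 vs 6 | 4/30 | −0.26 | −0.11 | −0.41 |
| 7 vs 6 | 8/30 | −0.42 | −0.26 | −0.57 |
| 7 vs 6 | 14/30 | −0.64 | −0.49 | −0.79 |

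For 7 vs 5 days, the favourable sign removes about 61%, 40% and 26% of the false effect as p rises. The other sign is worse than no offset in every row.

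**Step 4: week 4.** Its length is Month 1 minus 21 days: 14 + 16 − 21 = 9 nominally; 13 + 13 − 21 = 5 to 15 + 19 − 21 = 13 within visit allowances; 21 − 21 = 0 to 37 − 21 = 16 within the deviation limits. At a constant daily rate, a fully observed 9-day week 4 shows a false worsening against a 7-day week. With the favourable sign it is 0.42 − 0.25 = 0.17 to 1.27 − 0.25 = 1.02 on the logit scale (odds ratios about 1.2 to 2.8, depending on rate and threshold). With the other sign it is 0.42 + 0.25 = 0.67 to 1.27 + 0.25 = 1.52 (about 2.0 to 4.6).

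**Step 5: contrasts within a week.** If everyone has the same n in a week, log(n/7) is a constant. The categorical week effect absorbs it, and the arm contrast in that week does not change.

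**The case against.** The strongest reply is that little depends on this. The measure was added in SAP Version 3 and lies outside the primary and key secondary tests. Assignment is blinded, no document figure suggests that diary completion differs by arm, and months with compliance of 50% or less are set to missing (SAP 5.4.1). Step 5 shows that equal observed days leave the within-week arm contrast alone. The week 4 rule is explicit and uses all of Month 1, and the SAP states no test of week 4 against earlier weeks. All of this stands, and it limits the severity.

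Some stronger readings are tempting, but the documents do not support them:
- That the offset makes no correction. Signed toward higher counts, it removes part of the exposure effect (Step 3).
- That the offset is never zero in week 4. It uses compliant days, so a 9-day week with 7 diary days gives log(7/7) = 0, as does a complete 28-day Month 1.
- That this analysis establishes onset of effect. SAP 5.5.10.1 and 5.5.10.3 define onset by month, from the monthly models; no visible section ties the weekly measure to it.
- That week 4 treatment comparisons are distorted in every arm. The distortion is between weeks; between arms it needs unequal observed days.

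What the reply does not answer is that the exposure adjustment does not fit its link and its direction is left open. The monthly 50% rule also does not prevent a sparse or empty week within a retained month.

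**Conclusion.** The specification is wrong as written, at low severity. At the assumed rates the offset supplies 0.25 where 0.42 to 1.27 is needed for 9 days, and −0.34 where −0.50 to −1.73 is needed for 5. If lower counts are modelled, it goes the wrong way. Comparisons of week 4 with earlier weeks are distorted. Treatment contrasts within a week are essentially unaffected unless observed days differ between arms, and the documents do not show that they will.

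The sizes rest on daily rates taken from the eligibility range, independent days, and fits without the planned random intercept. That the offset is not exact under a cumulative logit does not depend on the particular rates chosen.

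**What to change.** Replace the ordinal model in SAP 5.5.10.3 with the repeated-measures negative binomial form of 5.5.10.2, with week in place of month and log(compliant days/7) as the offset. Alternatively, model migraine days out of compliant days as binomial. Exclude weeks with no compliant days, and say so.

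If the ordinal model is kept, state which direction is modelled and enter log(compliant days) as a covariate with an estimated coefficient instead of a fixed offset. This is still approximate, because the shift needed differs by threshold.

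Limiting week 4 to days 22 to 28 is optional once exposure is modelled correctly. It would match the 7-day definition, but it drops the later days of Month 1 and does not equalise exposure when Month 1 is shorter than 28 days.

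The cost is a change of SAP wording, to be made before unblinding (Protocol 9.2), and a change of effect scale from an odds ratio on the weekly count to a rate ratio or a daily odds ratio. The SAP specifies the monthly negative binomial model but does not show that it is already programmed, and it provides for non-convergence there. The weekly version needs a similar fallback.
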